The Investigator's Protocol

1. Title

Benefit of lumbar bracing for chronic low back pain due to degenerative disc disease

2. Principal Investigator and Co-Investigators

[name]

3. Sponsor of the Study

The Foundation of Physical Medicine and Rehabilitation

4. Investigational New Drug (IND) / Investigational Device Exemption (IDE)

None

5. Purpose of the Study, Including the Hypothesis to be Tested

The main objectives of this study are to evaluate the benefits of back bracing in the symptomatic management of patients with CLBP due to degenerative lumbar disc disease. We plan to study patients with uncomplicated CLBP without symptoms of radiculopathy or neurogenic claudication.

The secondary objectives of the study are to evaluate if a back brace provides any additive benefit to usual care consisting of exercise and patient education in patients with CLBP due to degenerative disc disease.

Specific Aim 1. To evaluate the effectiveness of back brace to improve pain and patient-reported functional measures in patients with uncomplicated CLBP due to degenerative disc and degenerative joint disease without associated symptoms of neurogenic claudication or lumbosacral radiculopathy.

Hypothesis 1. Back brace in addition to usual care will provide statistically significant improvement in pain and functional measures compared to usual care alone.

Specific Aim 2. To evaluate the adherence to back brace wear instructions in patients with uncomplicated CLBP due to degenerative disc and degenerative joint disease without associated symptoms of neurogenic claudication or lumbosacral radiculopathy

Hypothesis 2. Patients with CLBP, due to degenerative disc and degenerative joint disease without associated symptoms of neurogenic claudication or lumbosacral radiculopathy, who are prescribed a back brace, will demonstrate clinically acceptable rates of adherence to brace wear instructions.

6. Background and Results of Previous Related Research

Physiatrists use back braces (lumbar support, back corset, semi-rigid brace, and lumbar orthotic) for symptomatic management of patients' chronic low back pain (CLBP) despite very poor evidence supporting their use in the few published studies that have examined them. Evidence supporting back braces in other populations, such as pregnant women, and patients with sub-acute or acute low back pain, is better established. (Pennick, 2013; Calmels, 2009; Podichetty, 2008) However, the benefits of back braces in the CLBP population are very unclear.

A Cochrane review on the role of lumbar supports in treating chronic LBP revealed that limited evidence was available, which led to their conclusion that "it remains unclear whether lumbar supports taxas beautificate system

than no or other interventions for treating low-back pain." (van Duijvenbode, 2008) They emphasized the need for high quality randomized trials evaluating the effectiveness of back braces, and also recommended that compliance of brace wear be monitored.

The mechanism by which back braces might help patients with CLBP is also unclear. The semi-rigid design of the commonly used back brace does not mechanically limit movement enough to suggest that movement limitation is the mechanism by which back braces provide relief. However, some studies have suggested that back braces help patients with CLBP by providing postural support or a kinesthetic reminder of their posture. Using posturography, Munoz et al., studied the forces applied by lumbar bracing and concluded that back braces seem to help by improving the quality of balance strategy used by the patient. (Munoz, 2010) Another mechanism by which back braces are believed to help patients is by providing warmth underneath the brace.

There is poor published information regarding adherence to instructions (compliance) about the use of back braces. Based on our anecdotal clinical experience we find that adherence rates vary widely among our patients who are prescribed back braces, ranging from non-use to constant use around the clock. Poor adherence to instructions can be a significant factor resulting in inconclusive evidence supporting the role of back brace in patients with CLBP. A recent study showed that a strong predictor for consistent adherence to back brace usage was a positive attitude towards it. In this study, positive attitude towards the back brace explained 41% of the variance in outcomes. In addition, they found that perceived benefit from the brace outweighed any subjective discomfort. (Roelofs, 2010)

Back braces have been used as adjunctive therapy in addition to other conservative care options. A recent study evaluated the cumulative effect of bracing to exercise and found that bracing helps to increase trunk stiffness and augments muscle contractions, which may remind the patients to better comply with exercise instructions. (Aleksiev, 2014) This suggested a potential synergistic effect of bracing and exercise in the management of patients with CLBP.

7. Definition of the Population to Which the Study is Directed, with Justification

Patients with CLBP who have been referred to the PM&R Spine clinic will be the population from which the study subjects will be recruited from. Patients with CLBP are referred from primary care clinics and other specialty clinics within the VA North Texas Health Care System.

8. Subject Selection	, Inclusion and	Exclusion	Criteria
----------------------	-----------------	-----------	----------

Inclusion	Exclusion
18-85 years of age	Lumbar radiculopathy
Diagnosis of lumbar degenerative disc disease or	Neurogenic claudication
joint disease	Spondylolisthesis with instability
Low back pain > 6 weeks	Previous lumbar spine surgery
Uncomplicated low back pain without symptoms	Recent (<1 year) brace use or physical therapy

VA North Texas Health Care System IRB NUMBER: 15-088 IRB APPROVAL DATE: 01/02/2018

of pain radiating below the knee	program
	No active psychiatric illness

All patients will need to have a radiograph (x-ray) or magnetic resonance imaging (MRI) of the lumbosacral spine on file within 1 year of their enrollment into the study. No X-rays or MRIs will be ordered specifically for screening purposes for this study. Patients with no X-rays or MRIs available for review will be excluded from the study. Once the targeted patients are identified, and they agree to participate in the study and sign an IRB-approved informed consent document, they will undergo initial history and physical examination. Their radiological images will be reviewed and applicability of study criteria will be documented.

9. Number of Subjects in the Study

In this study, we plan to recruit 120 adult subjects.

We powered the study based from previous data we collected and published using the PDQ. ([name], 2012) In that study, we observed a mean difference between the two study groups of 8 points on the PDQ total score.

Using other PDQ data obtained from a different study by one of the authors, we found a standard deviation of 18 for the PDQ functional subscale. We would expect a change in function as sign of improvement in the proposed study, so we calculated a power analysis based on a moderate effect size of 0.44 to 0.5 (Cohen's d).

Using G-Power analysis software, for a one-tailed probability (since we expect only improvement, not worsening) and effect size d of 0.5, with an alpha error of 0.05 and a power (1- β error probability) of 0.8, we would expect a difference in mean score between the 2 randomized groups to be detectable with a sample size of 51 subjects in each group, total sample size of 102. Estimating a 15% drop out rate, we would need 60 subjects in each group, for a total sample size of 120.

10. Justification for the Use of Vulnerable Populations

Vulnerable patients will not be enrolled in this study.

11. Study Design

This is a prospective, randomized controlled trial. Blinding of the subjects is not possible because a back brace is a visibly obvious intervention. In addition, since we are evaluating the adherence of back brace wear, blinding of the investigator is also not possible. Therefore, this study will be an unblinded RCT.

12. Description of Procedures to be Performed

Patients will undergo baseline assessment of function, pain and quality of life (QOL) by completing the following paper-based questionnaires and assessments:

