Brace Wear Instruction: Patients will be instructed to wear the brace during work (if applicable) or during their typically symptomatic periods. They will be instructed to wear the brace at least once a day-for 30minutes, up to 6 hrs/day (maximum). The back brace will be replaced within the study period for any unusual wear/tear as necessary.

All treatment group patients will be provided with a diary in which they will document the number of hours they wore the brace on each day and document adverse events, if any. All control group patients will be asked to document in a diary their pain and exercise routine.

Time Points

Study patients will be assessed at the following time points:

a) Baseline

b) A brief, phone call at 3 weeks to assess any reports of adverse events or concerns of brace wear in patients IRB NUMBER: 15-088

IRB APPROVAL DATE: 01/02/2018

in the treatment group.

c) The 6-week time point will be our primary end-point. At this point, all study patients including patients in the treatment group and the control group will undergo all assessments they underwent at the baseline visit.

d) Our secondary end-points will be at 12-weeks and 6-months during which we will re-administer all baseline assessments as well as obtain a narrative report on additional interventions or treatments that the patients might have sought and/or obtained in the interim. These assessments will be conducted telephonically by our research coordinator.

Patients will be requested not to undergo any additional treatments and interventions during the 6-week period of back school. We will coordinate with their spine & pain clinic providers as well as with their primary care clinics to ensure compliance with the study protocol during this period.

13. Anticipated Data and Data Analysis

We will perform descriptive statistical analysis to evaluate baseline variables and demographics of all study subjects. We will use appropriate inferential analyses to evaluate for differences in outcome measures between the study and control groups. For all statistical analyses, we plan to use Stata 13 (College Station, TX).

14. Provisions for Managing Adverse Reactions

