b. The VA data will be combined with non-VA (UTSW) data received using the REDCap data input center. [name] will analyze the combined, de-identifed data, at the VA location.

c. Baseline study visit/surveys and back school with be done at UTSW for all UTSW patients. VA patients will receive the same care at the VA. After the initial visit, UTSW patients will be contacted for follow-up surveys by the VA research coordinator.

d. This is a pre-existing protocol at the VA. UTSW (Parkland) will be joining this research effort, but all data ownership remains with the VA. However, no data from UTSW (Parkland) has been collected to date. All data collected will be stored and maintained at the VA site.

e. As the data will only be collected at the VA, the VA will assume all data ownership. The UTSW (Parkland) investigators will be given opportunity to opt-in for authorship credit.

2. Since data will only be transferred from UTSW (Parkland) to the VA, no changes to the informed consent or HIPAA authorization are necessary.

Multi-Center Research

This is not a multi-center research study.

RESEARCH	ACTIVITIES FOR VA RESEARCH These activities MUST be approved by the VA R&D Committee		ACTIVITIES FOR NON-VA RESEARCH	Explain how VA and NON-VA activities of Dual-Appointment
	VA Site	Non-VA Site	NOT be approved by the VA R&D Committee	distinguished
Advertising				
Recruitment	X	X		
Research-related medical procedures to be performed (LIST)				
Other interventions or interactions with living individuals to be performed (LIST)	Back school – 2 sessions covering back anatomy and physical therapy, follow- up surveys	Back school – 1 session covering back anatomy and physical therapy		
Clinics, labs, other units to be used (LIST)				
PHI Use	X			
PHI Disclosure	X			
Data Coordinating Center	X			
Members of Research Team (LIST)	[name], MD [name]	[name], [name], [name], [name], [name], [name]	VA North	Texas Health Care Syste

1. Summary of Activities for "Collaborative" Research

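### Evaluating brace adherence does not justify an unmasked analyst or unprotected outcome collection; coded arms and a fixed question order would remove some avoidable bias

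*Combined protocol and SAP*

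**What the plan says.** Section 11 (Study Design) gives two reasons and one conclusion.

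- Subjects: "Blinding of the subjects is not possible because a back brace is a visibly obvious intervention".
- Investigator: "since we are evaluating the adherence of back brace wear, blinding of the investigator is also not possible".
- Conclusion: "Therefore, this study will be an unblinded RCT".

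No masking of the person who collects outcomes, or of the analyst, is mentioned.

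Section 12 describes how the data arise. Treatment-group patients are "provided with a diary in which they will document the number of hours they wore the brace on each day", and the same diary takes adverse events. Control patients keep a different diary, covering pain and exercise. At baseline the questionnaires are on paper and completed by the patient. The 6-week primary time point repeats the baseline assessments, without stating the mode or who collects them. For the 12-week and 6-month time points the protocol says: "These assessments will be conducted telephonically by our research coordinator". Those contacts also take a narrative of other treatments, in no stated order. The treatment group alone receives "A brief, phone call at 3 weeks to assess any reports of adverse events or concerns of brace wear in patients"; the caller is not identified.

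The collaborative-research pages at the end of the protocol add that, after the initial visit, "UTSW patients will be contacted for follow-up surveys by the VA research coordinator" (item c), and that one person "will analyze the combined, de-identifed data, at the VA location" (item b).

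Section 13 says only that suitable inferential methods will compare the groups. It names no test, model or primary scale.

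**The concern.** Every outcome here is a patient's own report: PDQ, PROMIS scales, EQ-5D and a pain rating. Since patients know their arm, some expectation bias cannot be avoided, which makes the avoidable part worth removing. Two avoidable routes remain open.

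The first is the analyst. With many scales, three follow-up times and no fixed test or primary scale, someone who sees the arm labels can settle on the scale or test that looks best, even without intending to. This route affects all patients at all time points.

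The second is the interviewer. Someone who knows the arm, or who has just discussed the brace or other treatments, can influence spoken answers. This route is narrower, because telephone collection is stated only for the secondary time points.

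The only reason given for leaving both routes open is adherence evaluation, and that reason reaches neither of them.

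**Working it through.** **Step 1. Does the adherence reason reach the analyst and the outcome collection?**

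| Question | What the protocol provides | Consequence |
|---|---|---|
| Who records adherence? | The patient, in a diary (section 12) | The outcome collector need not ask about it before the scales are done |
| What does the analyst receive? | De-identified combined data (item b) | Arm labels can be coded in the same export |
| Which data reveal the arm? | Brace diary, control-group exercise diary, adverse events on brace wear, 3-week call records | All must be held back; withholding the brace diary alone would leave the control-only diary to show the arm |
| Who collects outcomes at 6 weeks? | Not stated in section 12; for UTSW patients, contact by the VA coordinator (item c) | Self-completion fits the paper baseline but needs to be stated |
| Who collects at 12 weeks and 6 months? | The research coordinator, by telephone | Question order and verbatim reading matter |

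The adherence reason can explain why an investigator handling brace diaries knows the arm. It does not explain why the analyst must, or why outcomes cannot come first in each contact.

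**Step 2. The plan's own sample size.** Inputs from section 9: d = 0.5, one-tailed alpha 0.05, power 0.80, 15% dropout.

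- The exact one-sided t calculation gives 51 per group (power 0.806), as stated.
- 51 / 0.85 = 60 per group, or 120 in total, as stated.

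Masking changes neither figure.

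**Step 3. Illustration of what a shift would do.** The documents give no size for interviewer or analyst bias, so the shift *b* is assumed. Inputs: SD 18 (PDQ functional subscale, section 9), 51 per arm, one-sided 5% level, no true effect.

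SE = 18 × √(2/51) = 3.56 points.

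False-positive rate = P(Z > 1.645 − b/3.56).

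| Assumed shift b (points) | 1.645 − b/3.56 | One-sided error |
|---|---|---|
| 0 | 1.645 | 5.0% |
| 1 | 1.364 | 8.6% |
| 2 | 1.083 | 13.9% |
| 3 | 0.802 | 21.1% |

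A noncentral t calculation agrees: shifts of 0.05, 0.10, 0.15 and 0.20 SD (0.9, 1.8, 2.7 and 3.6 points) give 8.2%, 12.6%, 18.6% and 26.1%.

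**Step 4. Limits of the illustration.** It models a mean shift in scores, so it says nothing about selection among scales or tests by the analyst, which is not quantified here. It does not separate interviewer influence from bias in unblinded patients. The shifts are not expressed as a share of the 8-point difference in section 9, because that difference is for the PDQ total score and the SD of 18 is for the functional subscale.

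**The case against.** The strongest case on the other side is that the dominant bias comes from patients, who cannot be blinded for a sound reason and who produce every score. They may also reveal their arm on the telephone. Nothing proposed here removes that. This stands, and it limits what the fix can claim.

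Several stronger readings are tempting, and the documents do not support them.

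- *Adherence is the excuse for unblinding everyone.* It is not. Section 11 cites it for the investigator only.
- *Existing staff could mask the interviewer.* This is not shown. One research coordinator role is described, the 3-week caller is not identified, and team names are removed. Question order and self-completion reduce influence but are not masking.
- *The primary end-point is taken by telephone interview.* Section 12 attaches the telephone to 12 weeks and 6 months. For VA patients, 6-week self-completion on paper looks like the existing intention. For UTSW patients, item c says only that they are contacted for surveys, and their number is not given.
- *The analysis will be one-sided.* Section 9 uses a one-tailed power calculation; section 13 does not state the sidedness of the test.

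It can also be said that a locked analysis plan would solve most of the analyst problem without coded arms. That is largely right, but no such plan is in the documents, and coding protects the choices made until one is locked. Finally, some text on data storage was removed before review, so this point makes no claim about how files are currently held.

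**Conclusion.** The point holds in limited form. Subjects are unblinded for a valid reason. The adherence reason, however, does not justify an analyst who sees the arms or follow-up contacts with no protected order of questions. The analyst route matters most, because it touches all the data and the analysis is left open. The interviewer route is clear at 12 weeks and 6 months and possible for UTSW patients at week 6.

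The size of the bias is unknown. The rise from 5% to about 9% to 21% rests on assumed shifts of 1 to 3 points, SD 18, 51 per arm, a one-sided test and no true effect. A reader might take it as an estimate of the harm, or of what the fix would save. It is neither: the fix would remove only part of any such shift. This is an inexpensive improvement that should be made; it does not undermine the design.

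**What to change.** Replace the investigator-blinding sentence in section 11, and cross-refer from sections 12 and 13, with wording such as:

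> Patients and treating clinicians are unblinded. The analyst works with arms coded A and B until the primary outcome, the statistical test and the analysis program are locked. Until then, all data that reveal the arm (brace diary, control-group exercise diary, adverse events and 3-week call records) are held in a separate file. At every follow-up the outcome questionnaires are completed before any question on brace use, adverse events or other treatments. The 6-week primary questionnaires are self-completed in both arms and at both sites where possible; the telephone is the fallback, and items are then read verbatim. These steps limit analyst and interviewer influence. They do not mask the interviewer or remove bias from unblinded patients, which is a limitation of the trial.

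The separate file concerns the analyst's data only; it does not change who sees adverse events for patient care. The 7-day pain rating used as an outcome stays in the outcome file.

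Cost: protocol wording, a coded export from REDCap (already in use), a call script, a little more data handling and some reminder calls. The core steps need no second assessor and no change in sample size. Because the protocol is already running at the VA, the mode of each 6-week assessment should be recorded in case modes become mixed.

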Brace Wear Instruction: Patients will be instructed to wear the brace during work (if applicable) or during their typically symptomatic periods. They will be instructed to wear the brace at least once a day-for 30minutes, up to 6 hrs/day (maximum). The back brace will be replaced within the study period for any unusual wear/tear as necessary.

All treatment group patients will be provided with a diary in which they will document the number of hours they wore the brace on each day and document adverse events, if any. All control group patients will be asked to document in a diary their pain and exercise routine.

Time Points

Study patients will be assessed at the following time points:

a) Baseline

b) A brief, phone call at 3 weeks to assess any reports of adverse events or concerns of brace wear in patients IRB NUMBER: 15-088

IRB APPROVAL DATE: 01/02/2018

in the treatment group.

c) The 6-week time point will be our primary end-point. At this point, all study patients including patients in the treatment group and the control group will undergo all assessments they underwent at the baseline visit.

d) Our secondary end-points will be at 12-weeks and 6-months during which we will re-administer all baseline assessments as well as obtain a narrative report on additional interventions or treatments that the patients might have sought and/or obtained in the interim. These assessments will be conducted telephonically by our research coordinator.

Patients will be requested not to undergo any additional treatments and interventions during the 6-week period of back school. We will coordinate with their spine & pain clinic providers as well as with their primary care clinics to ensure compliance with the study protocol during this period.

13. Anticipated Data and Data Analysis

We will perform descriptive statistical analysis to evaluate baseline variables and demographics of all study subjects. We will use appropriate inferential analyses to evaluate for differences in outcome measures between the study and control groups. For all statistical analyses, we plan to use Stata 13 (College Station, TX).

14. Provisions for Managing Adverse Reactions

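### No planned record collects adverse events or exercise in the same way in both arms before the 6-week primary endpoint; a common diary would be a cheap, low-priority improvement

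*Combined protocol and SAP*

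**What the plan says.** **Diaries (Section 12, Brace Wear Instruction).** Patients in the brace arm receive a diary in which to "document the number of hours they wore the brace on each day and document adverse events, if any". The next sentence sets the control diary: "All control group patients will be asked to document in a diary their pain and exercise routine". No frequency is stated for the control diary.

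**Week 3 (Section 12, Time Points, item b).** The plan provides "A brief, phone call at 3 weeks to assess any reports of adverse events or concerns of brace wear in patients". A page stamp interrupts the sentence there, and it resumes by naming the treatment group.

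**Week 6 (item c).** "The 6-week time point will be our primary end-point". Patients in both arms "will undergo all assessments they underwent at the baseline visit". Section 12 lists these as a 7-day numerical pain diary, the PDQ, the PROMIS instruments and the EQ-5D.

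**Week 12 and month 6 (item d).** The same battery is repeated, and staff also "obtain a narrative report on additional interventions or treatments that the patients might have sought and/or obtained in the interim". No such report is listed at week 6. For the first six weeks the plan relies on a request, "Patients will be requested not to undergo any additional treatments and interventions during the 6-week period of back school", and on coordination with the spine and pain clinics "as well as with their primary care clinics to ensure compliance with the study protocol during this period".

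**Elsewhere.** Section 5 makes exercise and education the usual care given to both arms. Section 6 cites work suggesting that a brace may prompt patients to follow exercise advice. Section 14 expects pain and discomfort from the brace, and has unexpected events reviewed individually as they arise. Section 16 states that there is no data safety monitoring plan or board.

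**The concern.** Both arms keep a diary, but the diaries ask for different things, and the difference goes beyond what the adherence aim requires. Hours of wear can only be logged by patients who were given the brace. That does not explain why brace patients are not asked about exercise, or why controls are not asked about adverse events.

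Two things are at stake.

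- **Adverse events.** The expected harm of the brace is pain and discomfort, and every patient enters with back pain. A count of such reports solicited in one arm is hard to read without a count solicited in the same way in the other.
- **Exercise.** It is part of the care both arms share, and the protocol's own background links it to bracing. Whatever the trial finds, readers will ask how much patients in each arm exercised. The plan would answer for controls only.

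A smaller, separate matter affects both arms alike. Patients are asked to avoid other treatment through week 6, but their own account of whether they did is not scheduled until week 12.

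**Working it through.** The plan's only computed figure is the sample size in Section 9. It reproduces: for d = 0.5, one-sided alpha 0.05 and power 0.80, the two-sample t test needs 50.15, so 51 per group, and 51 / (1 − 0.15) = 60 per group. The present point does not depend on it, except that about 60 patients per arm would keep each diary. No other arithmetic applies, so the check sets the planned sources side by side.

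| Item, baseline to week 6 | Brace arm | Control arm |
|---|---|---|
| Hours of brace wear | Diary, daily | Not applicable |
| Adverse events | Diary, plus the 3-week call | No scheduled collection described |
| Exercise | No record described | Diary, frequency not stated |
| Pain in the follow-up diary | Not mentioned | Diary, frequency not stated |
| 7-day pain diary at baseline and week 6 | Yes | Yes |
| PDQ, PROMIS, EQ-5D at baseline and week 6 | Yes | Yes |
| Patient report of other treatments | Not before week 12 | Not before week 12 |

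1. **Does the week-6 visit close the gap?** No. It repeats the baseline battery, and none of the listed instruments is described as an exercise log or an adverse-event enquiry.
2. **Does Section 14 close it?** No. The individual review of unexpected events is not confined to one arm, so a control's spontaneous report could be captured. But the section schedules no enquiry.
3. **Does the 3-week call close it?** Rejoined across the page stamp, the sentence places the call in the treatment group. The closing words could conceivably qualify only the brace concerns, leaving adverse events to be asked of everyone. Even on that reading the adverse-event diary remains one-sided and exercise is untouched.
4. **Is pain affected in the same way?** No. The 7-day diary and the PROMIS pain instruments are collected identically in both arms at baseline and week 6.

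Two rows of the table, adverse events and exercise, therefore have a planned source in one arm and no equivalent in the other.

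**The case against.** The strongest case against is that nothing the trial sets out to test depends on these records. Hypothesis 1 compares brace plus usual care with usual care alone. Exercise after randomisation follows allocation, so it is not a baseline confounder. If the brace leads patients to exercise more, that is part of the effect being tested, and no mediation aim is stated. Section 13 plans no between-arm analysis of exercise or adverse events. Discomfort from wearing a brace has no literal control counterpart, controls' background pain is recorded, and Section 15 classes the risk as minimal. **This stands**, and it is why the point ranks low.

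Three stronger readings are tempting, and the documents support none of them.

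- *The differing diaries bias the primary result.* The trial is unblinded and its outcomes are self-reported, so a reader might infer this. But both arms keep a diary, attend back school and complete the same 6-week battery, and nothing in the documents gives a size or direction for such a bias.
- *Adverse events and exercise cannot be compared at all.* This is too strong. Spontaneous control reports may surface under Section 14. What is missing is a planned record made in the same way in both arms.
- *Departures from the treatment restriction before week 6 will go unseen.* Clinic coordination may reveal some, and the 12-week report may reach back that far. They would, however, be reported late and from memory.

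What survives is narrower. The asymmetry is a stated procedure, not an omitted detail. Aim 2 explains only the wear-hours entry, and daily records cannot be reliably reconstructed afterwards.

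**Conclusion.** The point holds as a low-priority improvement to the records. If the plan is followed as written, adverse events will be solicited in the brace arm and not in the control arm, and exercise will be recorded in the control arm and not in the brace arm, up to the primary endpoint.

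The effect on the primary analysis is not quantifiable, and none is claimed; the randomised comparison of pain and function remains valid. The loss is in interpretation: there will be no like-for-like control rate beside brace-arm pain and discomfort, and no description in both arms of the uptake of an element of usual care that Section 6 says bracing may influence.

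This rests on two assumptions: that the 3-week call is for the treatment group, as the rejoined sentence reads, and that no document outside the available text, such as a diary form or case report form, already asks both arms the same questions.

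**What to change.** 1. **Common diary.** Give both arms one form covering pain, exercise and adverse events, completed at the same stated frequency. Add hours of wear in the brace arm only.
2. **One question at week 6.** Ask both arms what other treatments they have obtained since baseline, including any brace. Asking once, at the endpoint, is preferable to a recurring brace-use item in the control diary, which could suggest bracing to unblinded controls and so encourage contamination.
3. **Optional.** Put the 3-week adverse-event questions to controls as well, keeping the questions about brace concerns for the brace arm. This adds about 60 brief calls. If the call stays in one arm, the common diary supplies the comparable adverse-event record.

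**Cost.** Items 1 and 2 need a revised form and one added question, and place a slight extra burden on patients. An exercise log may itself prompt exercise, but it would do so equally in both arms. The sample size and the primary analysis do not change.
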